1.4 Endpoints

1.4.1 Primary Endpoint

The primary endpoint is the 12-month serious adverse event rate for subjects receiving the permanent DRG IPG.

1.4.2 Secondary Endpoints

Secondary endpoints include:

- Percent change from baseline to 12 months post-permanent implant for overall pain intensity measured using the Visual Analog Scale (VAS)

Statistical Analysis Plan

- Change from baseline to 12 months post-permanent implant for physical function measured using the PROMIS-29 Profile
- Change from baseline to 12 months post-permanent implant for quality of life measured using the PROMIS Global Health Scale

1.4.3 Descriptive Endpoints

Safety

- Proportion of subjects with device, procedure or stimulation-related serious adverse events and non-serious adverse events among subjects who receive the permanent implant
- Proportion of subjects who have adverse events related to the trial implant procedure among subjects who fail the trial neurostimulator phase
- Summary of procedure-related serious adverse events and non-serious adverse events by implanter experience

Effectiveness

- Percent change from baseline to 1, 3, and 6 months post-permanent implant for overall pain intensity measured using the Visual Analog Scale (VAS)
- Change from baseline to 1, 3, and 6 months post-permanent implant for physical function measured using the PROMIS-29 Profile
- Change from baseline to 1, 3, and 6 months post-permanent implant for quality of life measured using the PROMIS Global Health Scale
- Change from baseline to 1, 3, 6 and 12 months post-permanent implant for neuropathic pain measured using the Neuropathic Pain Scale (NPS)
- Change from baseline to 1, 3, 6 and 12 months post-permanent implant for sleep disturbance anxiety, depression, fatigue, ability to participate in social roles and activities, pain interference and pain intensity measured using the PROMIS-29 Profile Patient Global Impression of Change (PGIC) at 1, 3, 6 and 12 months post-permanent implant

1.5 Randomization

This is a single-arm study and no randomization is administrated.

1.6 Blinding

There is no blinding for the subjects or the Investigators.

2.0 ANALYSIS CONSIDERATIONS

2.1 Analysis Populations

Statistical Analysis Plan

2.1.1 Primary Endpoint Analysis Population

[REDACTED]

2.2 Statistical Methods

2.2.1 Descriptive Statistics for Continuous Variables

For continuous variables, results will be summarized with the numbers of observations, means, and standard deviations, with quartiles, minimums, maximums. The normality test may be performed for selected variables as appropriate.

2.2.2 Descriptive Statistics for Categorical Variables

For categorical variables, results will be summarized with subject counts and percentages/rates, and where specified in the table mockups, with exact 95% Clopper-Pearson confidence intervals, or otherwise will be specified.

2.2.3 Survival Analyses

Survival analysis will be conducted to analyze the primary endpoint. Subjects without events will be censored at their last known event-free time point. Survival curves will be constructed using Kaplan-Meier estimates. The 95% confidence interval will be estimated using log-log transformation.

2.3 Endpoint Analysis

2.3.1 Primary Endpoint

The hypothesis is stated as follows:

[REDACTED]

where p is the 12-month serious adverse event rate for subjects who receive the permanent Axium or Proclaim DRG IPG. The hypothesis will be tested at the 5% significance level.

The primary endpoint analysis will be conducted using Kaplan-Meier method on subjects who received the permanent Axium or Proclaim DRG IPG (primary analysis population). The serious adverse events include adverse events which occur after permanent implant and CEC adjudicates as serious events.

The primary endpoint includes all serious adverse events, including ones related to the neurostimulation device or procedure as well as any unrelated serious adverse events.

[REDACTED]

Statistical Analysis Plan

[REDACTED]

[REDACTED]

[REDACTED]

The 12-month (365 days) serious adverse event rate will be estimated using Kaplan-Meier method with a 95% upper confidence bound (UCB) estimated using log-log transformation. If the 95% UCB is less than the [REDACTED], the null hypothesis will be rejected.

[REDACTED]

[REDACTED]

2.3.2 Secondary Endpoints

2.3.3 Reduction in pain intensity (VAS)

The endpoint will test whether subjects achieve a clinically relevant change (mean percentage reduction of at least [REDACTED]) in VAS score at 12 months from baseline.

Percentage change in VAS score is calculated within each subject as:

$$\% \text{ Change in VAS score} = (\text{VAS at baseline} - \text{VAS at 12-month})/\text{VAS at baseline} * 100\%$$

The following hypothesis will be tested:

[REDACTED]

The hypothesis will be tested at the 5% significance level. The analysis will be carried out by calculating the 95% lower confidence bound (LCB) on the mean % Change in VAS from baseline to 12-month visit based on a t-distribution. If the 95% LCB is greater than [REDACTED], the null hypothesis is rejected. The analysis population of this secondary endpoint will include primary analysis population subjects who complete both baseline and 12-month VAS scales.

Statistical Analysis Plan

2.3.4 Change in Physical Function (PROMIS Physical Function score)

The endpoint will test whether there is a change in mean PROMIS-29 Physical Function domain scores at 12 months from baseline. Change in PROMIS-29 Physical Function domain score is calculated as:

Change in PROMIS-29 Physical Function domain score = (PROMIS-29 Physical Function domain score at 12-Month – PROMIS-29 Physical Function domain score at Baseline)

The following hypothesis will be tested:

The hypothesis will be tested at the 5% significance level. The analysis will be carried out by calculating the 95% LCB on the mean change in PROMIS-29 Physical Function domain score from baseline to 12-month visit based on a t-distribution. If the 95% LCB is greater than [REDACTED], the null hypothesis is rejected.

2.3.5 Change in Global Health (PROMIS Global Health score)

The endpoint will test whether there is a change in mean PROMIS Global Health Score from baseline to 12 months. Change in PROMIS Global Health Score is calculated as:

Change in PROMIS Global Health Score = (PROMIS Global Health Score at 12-Month – PROMIS Global Health Score at Baseline)

The following hypothesis will be tested:

The hypothesis will be tested at the 5% significance level. The analysis will be carried out by calculating the 95% LCB on the mean change in PROMIS Global Health Score from baseline to 12-month visit based on a t-distribution. If the 95% LCB is greater than [REDACTED], the null hypothesis is rejected. The analysis population for this secondary endpoint will include subjects who complete both baseline and 12-month PROMIS Global Health questionnaire, irrespective of IPG types.

2.4 Sample Size Calculations

Statistical Analysis Plan

2.5 Interim Analysis

No formal interim analyses are planned for this study. As such, no formal statistical rule for early termination of the trial is defined.

2.6 Timing of Analysis

After the last subject with a permanently implanted Axium or Proclaim IPG reaches the 12-month study visit or crosses the 12-month study visit window, the primary endpoint analysis will be conducted and reported to the FDA.

Statistical Analysis Plan

2.7 Study/Trial Success

[REDACTED]

2.8 Subgroups for Analysis

T [REDACTED]
I [REDACTED]
[REDACTED]

2.9 Handling of Missing Data

[REDACTED]

2.10 Poolability

[REDACTED]
I [REDACTED]
[REDACTED]

Statistical Analysis Plan

2.11 Multiplicity

There is no multiplicity adjustment planned for this study.

2.12 Adjustments for Covariates

Unless otherwise specified, no adjustments for covariates will be made for any of the variables in the analyses.

2.13 Sensitivity Analysis

[REDACTED]

[REDACTED]

[REDACTED]

[REDACTED]

[REDACTED]

3.0 DESCRIPTIVE ENDPOINTS AND ADDITIONAL DATA

3.1 Baseline and Demographic Characteristics

The following baseline and demographic variables will be summarized for the subjects enrolled: gender, age, ethnicity, race, primary diagnosis, visual analog scale (VAS), etc.

3.2 Adverse Events

All the adverse device effects, serious adverse device effects, UADEs, USADEs will be summarized for all subjects who enrolled in this trial in terms the number of events, the percentage of subjects with events and event rate as # event/patient-month per CEC adjudication.

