## Clinical Investigational Plan

inferiority between the DRG stimulation group compared to the SCS group with a pre-specified 10% non-inferiority margin. The study met the primary endpoint with statistically significantly more treatment successes in the DRG stimulation group compared to the SCS group at 3 months post permanent implant (81.2% vs. 55.7%, respectively;  $p = 0.0004$ ). This effect persisted at 12 months post implant (74.2% vs. 53.0%;  $p=0.0047$ ). Secondary and tertiary outcomes including percent change in VAS scores, change in SF-36 scores, change in Profile of Mood States (POMS) scores, and change in Brief Pain Inventory (BPI) scores were also suggestive of improvements in the group who received DRG stimulation compared to the SCS group.

The most commonly reported definitely-related adverse events (AEs) in the group who received DRG stimulation with the Axium Neurostimulator System in the ACCURATE IDE study were pain at the implantable pulse generator (IPG) pocket (14.5% of subjects) and loss of stimulation due to lead migration (11.8% of subjects). There were a total of 21 serious adverse events (SAEs) in 19 subjects reported in this study. The difference in overall rate of SAEs between the Axium and Control groups was not found to be statistically significantly different (Axium 10.5%, Control 14.5%,  $p=0.6248$ ). Additionally, the overall difference in the rate of SAEs during the system trial (Axium 1.3%, Control 3.9%,  $p=0.62$ ) and after the permanent implant (Axium 9.2%, Control 10.5%,  $p=1.0$ ) were not shown to be statistically significantly different. Only 1 serious adverse device effect (SADE; cardiac arrhythmia post-implant) was classified as possibly or definitely related to the device, procedure and/or stimulation in the group, which received the Axium Neurostimulator System. There were no reports of stimulation induced neurological deficits in either the control or Axium group at any point in the study.

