### 9.1.5 Serious Adverse Device Effect (SADE).

## 9.2 Assessing, Recording and Reporting AEs

Safety surveillance within this study and the safety reporting both performed by the investigator, starts as soon as the subject is consented for the study. The safety surveillance and the safety reporting will continue until the last investigational visit has been performed, the subject/investigator concludes his participation into the study or the subject/investigator withdraws the subject from the study, except as otherwise specified in the CIP.

Records related to the subject's subsequent medical course must be maintained and submitted (as applicable) to the Sponsor until the event has subsided or, in case of permanent impairment, until the event stabilizes and the overall clinical outcome has been ascertained. All AEs will be monitored until they are adequately resolved. The status of the subject's condition should be documented at each visit.

AE data will be collected throughout the clinical study and will be reported to the Sponsor on a dedicated case report form through the EDC system. Reportable events to sponsor are considered:

1. ***All SAEs (whether or not the event is device and/or procedure related)***
2. ***All procedure, device and/or stimulation-related AEs (whether or not the event is considered serious)***

Device, procedure, and stimulation-related AEs are defined as follows:

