## Clinical Investigational Plan

- Device-related: A malfunction or migration of any device component including leads, extensions, IPGs and accessories.
- Procedure-related: Biological reaction (hematoma, infection, pain, etc.) as a result of the surgical procedure to implant the device.
- Stimulation-related: Event known to be caused by stimulation from the device. Normally stimulation-related events resolve when the device is turned off or reprogrammed.

The investigator should report all SAEs to the Sponsor as soon as possible but no later than outlined below.

Clinical Site	Reporting timelines
All Sites	SAEs must be reported no later than 3 calendar days from the day the site personnel became aware of the event or as per the investigative site's local requirements, if the requirement is more stringent than those outlined.

The date the site staff became aware the event met the criteria of an SAE must be recorded in the source document.

The Investigator will further report the SAE to the local IRB/EC according to the institution's IRB/EC reporting requirements.

Adverse events that are not serious will be reported to the Sponsor, as soon as possible after the occurrence of the event.

Please reference Section 3 of this document for risk information and Section 9.3 for a complete list of adverse effects related to DRG Neurostimulation Systems.

For unexpected failure modes or unexpected for all AEs, the site should follow their standard reporting practices for medical device reporting (MDR). As defined in 21 CFR 803, a MDR reportable event (or reportable event) is an event that device user facilities become aware of that reasonably suggests that a device has or may have caused or contributed to a death or serious injury. A device user facility must report deaths and serious injuries that a device has or may have caused or contributed to, establish and maintain AE files, and submit summary annual reports to FDA.

The Investigator will assign degree of relatedness to the device for all SAEs and device, procedure and stimulation-related AEs based on NIH definitions as follows:

**Possibly Device/Procedure-Related:** (must meet at least **2** criteria)

- Has a reasonable temporal relationship to intervention,
- Could not readily have been produced by the subject's clinical state,
- Could not readily have been due to environment or other interventions,
- Follows a known pattern of response to intervention.

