### **24.0 CLINICAL EVENTS COMMITTEE (CEC)**

A Clinical Events Committee (CEC) will be responsible for providing an independent review and adjudication of all subject deaths and adverse events. The CEC will review adverse events and determine device and/or procedure relatedness and whether serious or not (ADEs, SADEs, and SAEs). The CEC will base their final adjudication on the information provided on the case report forms, medical records, and their clinical knowledge and experience. The committee will consist of a minimum of three (3) members, comprised of pain specialists with experience in medical device implants/studies. The CEC will meet on an as-needed basis, at a minimum twice a year, to assess individual events in the study. [REDACTED]

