3.5 Descriptive Endpoints or Additional Data

3.5.1 Descriptive endpoints

The following descriptive endpoints will be reported:

Safety

- Proportion of subjects with device, procedure or stimulation-related serious adverse events and non-serious adverse events among subjects who receive the permanent implant
- Proportion of subjects who have adverse events related to the trial implant procedure among subjects who fail the trial neurostimulator phase
- Summary of procedure-related serious adverse events and non-serious adverse events by implanter experience

Effectiveness

- Percent change from baseline to 1, 3, and 6 months post-permanent implant for overall pain intensity measured using the Visual Analog Scale (VAS)
- Change from baseline to 1, 3, and 6 months post-permanent implant for physical function measured using the PROMIS-29 Profile
- Change from baseline to 1, 3, and 6 months post-permanent implant for quality of life measured using the PROMIS Global Health Scale
- Change from baseline to 1, 3, 6 and 12 months post-permanent implant for neuropathic pain measured using the Neuropathic Pain Scale (NPS)
- Change from baseline to 1, 3, 6 and 12 months post-permanent implant for sleep disturbance, anxiety, depression, fatigue, ability to participate in social roles and activities, pain interference and pain intensity measured using the PROMIS-29 Profile
- Patient Global Impression of Change (PGIC) at 1, 3, 6 and 12 months post-permanent implant

The analysis population for these descriptive endpoints will include primary analysis population subjects with available data and no imputation will be implemented.

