5.0 ACRONYMS AND ABBREVIATIONS

Acronym or Abbreviation	Complete Phrase or Definition
ADE	non-serious Adverse Device Effects, which include device, procedure or stimulation related non-serious adverse events
AE	Non-serious Adverse Events not related to device, procedure or stimulation
CEC	Clinical Events Committee
CIP	Clinical Investigation Plan
CRF	Case Report Form
LCB	Lower Confidence Bound
SADE	Serious Adverse Device Effects, which include device, procedure or stimulation related serious adverse events
SAE	Serious Adverse Events not related to device, procedure or stimulation
SAP	Statically Analysis Plan
UCB	Upper Confidence Bound
VAS	Visual Analog Scale (mm)

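### Do serious events judged unrelated to the device go unreported because SAP 3.2 tabulates only device effects?

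*SAP*

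**What the plan says.** SAP 3.2 promises event counts, subject percentages and rates per patient-month, based on CEC adjudication. Its list of classes is explicit: "All the adverse device effects, serious adverse device effects, UADEs, USADEs will be summarized for all subjects who enrolled in this trial".

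The glossary in SAP 5.0 divides events by relatedness. ADE and SADE are the related classes. SAE is given as "serious Adverse Events not related to device, procedure or stimulation", and AE is likewise limited to unrelated events.

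SAP 2.3.1 defines the primary endpoint more widely. It takes in serious events related to the device or procedure "as well as any unrelated serious adverse events".

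The first descriptive safety endpoint in SAP 3.5.1 is "Proportion of subjects with device, procedure or stimulation-related serious adverse events and non-serious adverse events among subjects who receive the permanent implant". The other two concern events related to the trial implant procedure and to the procedure generally.

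On collection, protocol 9.2 makes reportable to the sponsor "All SAEs (whether or not the event is device and/or procedure related"). In the same section the investigator grades relatedness, with an intermediate grade of "Possibly Device/Procedure-Related". Under protocol 24.0 the CEC must "determine device and/or procedure relatedness and whether serious or not (ADEs, SADEs, and SAEs").

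**The concern.** The primary result is a single Kaplan-Meier proportion compared with 15.5%. A reader of the report to FDA would want to see which events make it up, and above all which were adjudicated unrelated. As published, SAP 3.2 omits exactly the class that SAP 5.0 calls SAE, and all three safety endpoints in SAP 3.5.1 are also restricted to related events. Unrelated serious events are therefore visible only inside an aggregate rate.

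Three further points add to the impression of a gap:

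- SAP 3.2 covers all enrolled subjects (up to 426), while the primary analysis covers permanent implants (319), so the two outputs cannot simply be subtracted.
- The protocol has three grades of relatedness, while the SAP glossary has two and does not place the middle one.
- The CEC's remit in protocol 24.0 names device and procedure relatedness, while the SAP classes also mention stimulation.

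If all this were real, the make-up of the primary endpoint could be settled after the data were seen, in an unblinded single-arm study.

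**Working it through.** The plan states no figure for this point, so the check compares the texts and then gauges the scale.

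**Which serious events appear where**

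| Output | Population | Related serious | Unrelated serious |
|---|---|---|---|
| Primary Kaplan-Meier rate (SAP 2.3.1) | permanent implants | yes | yes |
| Annual 12-month SAE rate (protocol 10.7) | permanent implants | yes | yes |
| First safety endpoint (SAP 3.5.1) | permanent implants | yes | no |
| Adverse-event summary (SAP 3.2) | all enrolled | yes | not listed |
| Mock tables (mentioned in SAP 2.2.2), SAP 2.13, SAP 3.5.2, parts of SAP 2.3.1 | redacted | unknown | unknown |

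Rows 1 and 3 share a population, because SAP 3.5.1 uses primary-analysis subjects with available data. Subjects with any serious event minus subjects with a related one therefore gives, approximately, those with unrelated events only. It is approximate because row 1 is a censored estimate and row 3 a proportion, and because row 3 does not say that it starts at permanent implant. Event terms and event counts are not recovered this way.

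**Scale, from the pivotal trial as reported in protocol 2.0**

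Inputs: 76 subjects per arm; serious-event rates in the device arm of 10.5% overall, 1.3% in the trial phase and 9.2% after permanent implant; 14.5% in the control arm; 19 subjects with a serious event in all. For the device arm the protocol adds: "Only 1 serious adverse device effect (SADE; cardiac arrhythmia post-implant) was classified as possibly or definitely related to the device, procedure and/or stimulation".

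1. Recover the counts: 8/76 = 10.5%, 1/76 = 1.3%, 7/76 = 9.2%, 11/76 = 14.5%. These agree with the text, since 8 + 11 = 19.
2. Expected subjects with a serious event among 319 implants: 319 × 7/76 = 29.4.
3. The related event is described as post-implant, so the matching share is 1 of 7, assuming it belongs to the 7 subjects with an event after permanent implant. Related: 29.4 × 1/7 = 4.2. Unrelated only: 29.4 × 6/7 = 25.2.
4. With the 287 subjects planned for the 12-month analysis: 287 × 7/76 = 26.4, of which 3.8 related and 22.7 unrelated only.
5. With an assumed related share of 25% or 50%, 319 implants give 29.4 × 0.75 = 22.0 or 29.4 × 0.50 = 14.7 unrelated only.

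**Effect on the primary result**

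SAP 2.3.1 writes its event definition out in words, covering related and unrelated events. The glossary's narrower SAE does not enter it. The acronym SAE does not appear in the legible body of the SAP outside the glossary, so no visible rule depends on that entry. The estimate, the 95% upper bound and the comparison with 15.5% are identical under either reading of SAP 3.2.

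**The case for a change.** The strongest case for a change is that SAP 3.2 is legible, is the only visible section headed Adverse Events, and spells out its classes in words, so it excludes unrelated serious events even if the glossary is ignored. The fix would cost one table from data already held, and fixing the relatedness boundary in advance is sound practice when nobody is blinded. The pivotal trial's own count combined possible and definite relatedness, so a convention was available to adopt.

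The narrow reading stands: the published text lists no breakdown of unrelated serious events by type or relatedness, and the glossary does not match SAP 2.3.1. Less survives of the rest:

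- The population mismatch applies to SAP 3.2 but not to the first endpoint in SAP 3.5.1, which is in implanted subjects.
- The intermediate grade belongs to the investigator's scale in protocol 9.2. SAP 3.2 works from CEC adjudication, whose scale is not visible, so no conflict between the two is shown.
- Protocol 24.0 has the CEC classify ADEs and SADEs. Protocol 9.1.4 defines an ADE by relation to use of the device, which reasonably covers stimulation.
- The missing definitions of UADE and USADE carry little weight, because the protocol's definitions section has visibly lost text.
- Redacted mock tables and additional data cannot be counted as absent. The glossary's four classes may well label rows in those tables, though that is inference.

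**Conclusion.** No change to the plan is needed. On the published text there is a small descriptive gap together with a glossary slip: SAP 5.0 narrows SAE to unrelated events, while SAP 2.3.1 and the protocol count all serious events. Neither alters who is counted in the primary endpoint, how the rate is estimated, or when the null hypothesis is rejected. The underlying events are reported to the sponsor and adjudicated. An analyst writing the report would list the serious events behind the primary rate and show their relatedness as a matter of course.

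The amount of information concerned is not trivial. On the pivotal pattern, about 25 of 29 implanted subjects with an event would have unrelated events only, and about 15 if half were related. These figures assume that the pivotal rate carries over and rest on a single related event, so they indicate scale only. The conclusion also depends on reading SAP 2.3.1 as written and on not treating redacted tables as missing.
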